### **2.4.2 Prior, concomitant and post therapies**

Prior and concomitant medications will be summarized in separate tables by treatment group.

Prior medications are defined as treatments taken and stopped prior to first dose of study treatment. Any medication given at least once between the day of first dose of randomized study treatment and within 84 days after the last dose will be a concomitant medication, including those which were started pre-baseline and continued into the period where study treatment is administered.

Medications will be presented in alphabetical order, by Anatomical Therapeutic Classification (ATC) codes and grouped by anatomical main group. Tables will show the overall number and percentage of subjects receiving at least one treatment of a particular ATC code and at least one treatment in a particular anatomical main group.

Significant prior and concomitant non-drug therapies and procedures will be summarized by primary system organ class and MedDRA preferred term.

Prior surgeries and procedures are defined as surgeries and procedures done prior to first dose of study treatment. Any surgeries and procedures done between the day of first dose of study treatment and within the date of the last study visit will be concomitant surgeries and procedures, including those which were started pre-baseline and continued into the period where study treatment is administered.

NSAID use will be summarized.

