3.1 Study design

This multicenter study uses a randomized, partially-blinded, active-controlled, parallel-group design in subjects with AS. A screening period (SCR) of up to 10 weeks before randomization will be used to assess eligibility followed by 104 weeks of treatment. Two follow-up visits at Weeks 112 and 120 will occur thereafter.

At baseline (BSL), approximately 837 subjects whose eligibility is confirmed will be randomized to one of three treatment groups (1:1:1).

- Group 1: secukinumab 150 mg [1 x 1.0 mL s.c. plus placebo (1 x 1.0 mL s.c.)] at BSL, Weeks 1, 2 and 3, followed by administration every four weeks starting at Week 4
- Group 2: secukinumab 300 mg (2 x 1.0 mL s.c.) at BSL, Weeks 1, 2 and 3, followed by administration every four weeks starting at Week 4
- Group 3: GP2017 (adalimumab biosimilar) 40 mg (1 x 0.8 mL s.c.) at BSL followed by administration every two weeks

[figure not shown]
Although study treatment (secukinumab vs GP2017) will be provided in an open-label fashion to the subjects, secukinumab study treatment will be blinded to the dose. Subjects in groups 1 and 2 will know that they are on secukinumab, but will be blinded to which treatment arm and will not know whether they are receiving secukinumab 150 mg or 300 mg. Subjects in the GP2017 treatment group will know that they are receiving GP2017 (adalimumab biosimilar) 40 mg. Sponsor blinding is described in [Section 5.4](#).

Although no subject will be restricted from receiving necessary rescue medications for lack of benefit or worsening of disease, if rescue treatment with prohibited medications (as described in [Section 5.5.8](#)) occurs, subjects may remain in the study but must discontinue study treatment. All subjects may remain in the study and should continue study-related assessments up to completion, regardless of whether they continue study treatment or not. Subjects who are deemed not to be benefiting from the study treatment based upon safety and efficacy assessments by the investigator or for any reason on their own accord will be free to discontinue study treatment only or any further participation in the study at any time.

[REDACTED]

Two follow-up visits are to be completed after last administration of study treatment for all subjects, regardless of whether they complete the entire study as planned or discontinue prematurely.

Figure 3-1 Study design

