5.2 Treatment arms

Subjects will be randomly assigned at the baseline visit to one of the following three treatment groups in a 1:1:1 ratio, with approximately 279 randomized subjects planned for each group.

- Group 1: secukinumab 150 mg
- Group 2: secukinumab 300 mg
- Group 3: GP2017 (adalimumab biosimilar) 40 mg

Subjects in both of the secukinumab dose groups will receive study treatment at BSL, Weeks 1, 2, 3 and 4 followed by treatment every 4 weeks through Week 100. Subjects in the GP2017 group will receive study treatment at BSL and every two weeks through Week 102. Subjects can self-administer all secukinumab / placebo and GP2017 doses as described in [Section 3.1](#) at the study site or at home, according to the assessment schedule in [Table 6-1](#) and [Table 6-2](#).

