5.6 Study completion and discontinuation

5.6.1 Study completion and post-study treatment

A subject will be considered to have completed the study when the subject has completed the last visit planned in the protocol.

Information on the subject's completion or discontinuation of the study and the reason for discontinuation of the study will be recorded on the corresponding CRF.

In any case, the investigator or site staff must contact the IRT as soon as possible to record the subject's study completion (Week F120) and/or discontinuation.

The investigator must provide follow-up medical care for all subjects who are prematurely withdrawn from the study, or must refer them for appropriate ongoing care. This care may include initiating another treatment outside of the study as deemed appropriate by the investigator. This treatment may be any non-biologic DMARD. In case of a biologic treatment, a waiting period of 3 months for a subject previously on secukinumab and 4 months for a subject previously on GP2017 before initiating the treatment is recommended; elimination of adalimumab may take up to 4 months ([Humira® SmPC](#)).

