9.3 Treatments

Study treatment

The analysis of study treatment data will be based on the safety set. The number of visits with injections received will be presented by treatment group.

The duration of exposure to study treatment will also be summarized by treatment group. In addition, the number and percentage of subjects with cumulative exposure levels (e.g., any exposure, ≥ 2 weeks, ≥ 4 weeks, ≥ 8 weeks, etc.) will be presented.

Prior and concomitant medication

Prior and concomitant medications will be summarized in separate tables by treatment group.

Prior medications are defined as treatments taken and stopped prior to first dose of study treatment. Any medication given at least once between the day of first dose of randomized study treatment and the date of the last study visit will be a concomitant medication, including those which were started pre-baseline and continued into the period where study treatment is administered.

Medications will be presented in alphabetical order, by Anatomical Therapeutic Classification (ATC) codes and grouped by anatomical main group. Tables will show the overall number and percentage of subjects receiving at least one treatment of a particular ATC code and at least one treatment in a particular anatomical main group.

Significant prior and concomitant non-drug therapies and procedures will be summarized by primary system organ class and MedDRA preferred term.

Prior surgeries and procedures are defined as surgeries and procedures done prior to first dose of study treatment. Any surgeries and procedures done between the day of first dose of study treatment and within the date of the last study visit will be a concomitant surgeries and procedures, including those which were started pre-baseline and continued into the period where study treatment is administered.

The number and percentage of subjects receiving prior and concomitant ankylosing spondylitis therapy will be presented by randomized treatment group as well as the reasons for stopping

their therapies (primary lack of efficacy, secondary lack of efficacy, lack of tolerability, other) and the total duration of exposure to ankylosing spondylitis therapies previously. NSAID use will be summarized.

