#### 2.5.4 Supportive analyses

Sensitivity analyses and supplementary analyses will be conducted in order to provide evidence that the results seen from the primary analysis are robust.

Sensitivity analyses will be conducted to determine the impact of missing data handling on the primary estimand.

- Tipping point analysis
- In case an imbalance in the distribution of any baseline demographics and disease characteristics impacting response (e.g., gender and smoking status) is seen, additional analyses may be performed adjusting for these variables in the model
- The unused models described in [Section 2.5.3](#) may be used for sensitivity analysis, if appropriate (e.g., if they converge).

Additional supplementary analyses may be conducted to examine different estimands which are also deemed clinically relevant, such as the estimand based on the hypothetical strategy which would examine the treatment effect in outcomes where biologic rescue was not available to subjects.

The effect of the COVID-19 pandemic on the study will be monitored and assessed. Additional supplementary analyses to study the potential effect of the pandemic on the primary estimands may be performed, and are described in [Section 2.15](#).

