## 4 Change to protocol specified analyses

No change from protocol specified analysis was made.

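### SAP 2.4.2 ends the concomitant-medication window 84 days after last dose where Protocol 9.3 runs it to the last visit, so later drug starts in early stoppers who stay in follow-up go untabulated

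*SAP*

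**What the plan says.** - **Protocol 9.3 (Treatments).** A medication is concomitant if given at least once from the day of first dose up to "the date of the last study visit will be a concomitant medication".
- **SAP 2.4.2 (Prior, concomitant and post therapies).** The start is the same but the end differs: a medication given "within 84 days after the last dose will be a concomitant medication". In the same section, surgeries and procedures still run to the last study visit. The section title mentions post therapies, but the visible text gives no rule or table for drugs started after the window.
- **SAP section 4.** "No change from protocol specified analysis was made". SAP section 1 says that deviations from the protocol are documented.
- **Treatment and visit schedule.** Protocol 5.2 has secukinumab at baseline and Weeks 1 to 4, "followed by treatment every 4 weeks through Week 100", and GP2017 "at BSL and every two weeks through Week 102". Protocol 3.1 adds: "Two follow-up visits at Weeks 112 and 120 will occur thereafter".
- **Subjects who stop early.** Protocol 5.5.6 lets a subject who starts a prohibited biologic stay in the study with study treatment stopped. Protocol section 6 encourages all who stop treatment to stay to F120 and to have the Week 104 X-ray.
- **Estimand and imputation.** SAP 2.5.1 uses the Week 104 outcome whether or not the randomized drug was continued. SAP 2.5.3 imputes missing outcomes of subjects who discontinued from subjects who stopped drug but have a Week 104 X-ray. SAP 2.5.4 allows an optional supplementary estimand for outcomes "where biologic rescue was not available to subjects".

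**The concern.** The two documents define one table differently, and the SAP says there is no difference. A programmer following the SAP would produce a by-arm medication table that stops short of what the protocol promised.

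The shortfall falls on a group that matters here. Under an estimand that disregards adherence, the Week 104 X-ray of a subject who stopped early reflects the assigned drug plus whatever was taken afterwards. The same subjects also supply the imputation model for missing outcomes. To interpret a difference between secukinumab and GP2017, a reader needs to know, by arm, what these subjects moved to and when. With the 84-day limit, drugs first started later than that, possibly long before the X-ray, are left out of the summary.

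**Working it through.** The 84 days is a stated rule, not a derived figure, so there is no calculation in the plan to reproduce. The check is calendar arithmetic on nominal visit weeks.

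**Inputs.** SAP window end: last dose + 84 days = 84/7 = 12 weeks (SAP 2.4.2). Primary X-ray: Week 104. Last visit: F120 (Protocol 3.1). Last planned dose: Week 100 for secukinumab, Week 102 for GP2017 (Protocol 5.2).

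**Formulas.** For a last dose in week L:
- the SAP window closes at week L + 12;
- uncovered days before the Week 104 X-ray = (104 − L − 12) × 7, or none if L is 92 or later;
- uncovered days to F120 = (120 − L − 12) × 7.

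| Last dose, L | SAP window closes | Uncovered before Week 104 | Uncovered to F120 |
|---|---|---|---|
| Week 24 | Week 36 | 68 × 7 = 476 days | 84 × 7 = 588 days |
| Week 52 | Week 64 | 40 × 7 = 280 days | 56 × 7 = 392 days |
| Week 76 | Week 88 | 16 × 7 = 112 days | 32 × 7 = 224 days |
| Week 100 (secukinumab to plan) | Week 112 | none | 8 × 7 = 56 days |
| Week 102 (GP2017 to plan) | Week 114 | none | 6 × 7 = 42 days |

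For subjects treated to plan, the lost period lies wholly after the Week 104 X-ray and has little bearing on efficacy. For early stoppers who stay in, much of it lies before the X-ray.

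**What is and is not lost.** A drug given at least once by day 84 is counted, even if it continues for years. Only drugs first given after day 84 are missed.

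**Does another table fill the gap?** Protocol 9.3 also planned a by-arm summary of prior and concomitant ankylosing spondylitis therapy. The current SAP 2.4.2 has none; the document history says those data are not collected. Apart from a summary of NSAID use, the general medication table is the only visible medication summary that could show switching by arm. The underlying records should exist: Protocol 5.5.6 and 5.5.7 require rescue medication and all medication after enrollment to be entered on the CRF.

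**The case against.** The strongest reply is that 84 days is the SAP's general on-treatment convention. It also governs exposure (2.4.1), treatment-emergent adverse events (2.8.1), laboratory data (2.8.2) and vital signs (2.8.3.1), so using it to define concomitant use is coherent. Further, a biologic whose start is the reason for stopping study treatment would ordinarily fall within 84 days of the last dose and be tabulated. Later starts would still appear in listings (SAP 5.3), and perhaps in the protocol-deviation table (SAP 2.3.1). Redacted sections may hold more. The biologic-rescue estimand is optional, and nothing says its subjects would be identified from this table. No hypothesis test uses the 84-day rule.

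Most of that stands, and it limits the size of the point. It does not remove it. An on-treatment convention suits safety attribution; it does not suit describing therapy under an estimand that uses outcomes long after treatment has ended. Nor does it explain the last-visit limit for procedures in the same section, or the declaration of no change.

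A reader might go further. Protocol 5.6.1 recommends "a waiting period of 3 months for a subject previously on secukinumab and 4 months for a subject previously on GP2017" before another biologic, and one could infer that every such switch is missed, and more so in the GP2017 arm. The documents do not support this:

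- The wait is a recommendation for subjects withdrawn from the study. For those who stop drug and stay in, Protocol 5.5.6 and Table 5-1 state no wait before another biologic.
- The length of a month is not fixed. For live vaccines after GP2017, Protocol 5.5.5 says four months and 5.5.8 says 16 weeks. At 28 days a month, 3 months is 3 × 28 = 84 days, and a start on day 84 is counted. At 30.44 days it is about 91. Four months is 112 to 122 days.
- A claim that none of these switches is captured assumes that every start falls after the limit, which is circular.
- The 20% of each arm in the sample-size section (0.20 × 279 ≈ 56) is not a count of stoppers. The 80% assumption combines completing treatment with having evaluable films at both time points.

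**Conclusion.** The point holds as an undeclared departure of SAP 2.4.2 from Protocol 9.3 with a specific consequence. In subjects who stop study treatment before Week 92 and remain in follow-up, drugs first started more than 84 days after the last dose are missing from the by-arm table. The uncovered stretch before the Week 104 X-ray is 476 days for a stop at Week 24 and 280 days for a stop at Week 52.

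This rests on nominal visit timing and on the subject staying in to Week 104. The documents give no figure for how many subjects will do so, or how many will start a biologic late, so the number affected cannot be stated. The effect is on interpretation: the planned table would not fully show what followed study treatment in each arm. No planned test or estimate would change. The conclusion does not depend on any recommended waiting period, and none is endorsed here.

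**What to change.** Either of two changes settles it.

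1. In SAP 2.4.2, restore the protocol's window for medications: first dose to the date of the last study visit, matching the rule already used there for procedures.
2. Keep the 84-day window, record the departure in SAP section 4, and add a by-arm table of biologic and targeted synthetic DMARD use started after study-treatment discontinuation, through the last visit.

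The first costs one sentence. The second costs one sentence and one table. Both use medication records that the protocol already requires on the CRF, and neither alters treatment, visits or any hypothesis test.

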## 2.5 Analysis of the primary objective

### 2.5.1 Primary endpoint

The primary efficacy objective is to demonstrate that the proportion of subjects on secukinumab (150 mg or 300 mg) with no radiographic progression is superior to GP2017 40 mg at Week 104. The analysis of the primary efficacy objective will be based on the following estimand:

- Population – defined through appropriate inclusion/exclusion criteria to reflect the targeted AS population
- Variable – binary response variable indicating no radiographic progression defined as a change from baseline in mSASSS at Week 104 of  $\leq 0.5$
- Intercurrent event – regardless of adherence to randomized treatment
- Population-level summary – difference in proportions of responders between the secukinumab and GP2017 arms

### 2.5.2 Statistical hypothesis, model, and method of analysis

The statistical hypothesis for no radiographic progression being tested is that there is no difference in the proportion of subjects with no radiographic progression at Week 104 in the secukinumab 150 mg or secukinumab 300 mg versus the GP2017 40 mg regimen.

Let  $p_j$  denote the proportion of subjects with no radiographic progression at Week 104 for treatment regimens  $j, j=0, 1$  or  $2$  where

- 0 corresponds to GP2017 40 mg regimen,
- 1 corresponds to secukinumab 150 mg
- 2 corresponds to secukinumab 300 mg

In statistical terms,  $H_0: p_j = p_0, H_{Aj}: p_j \neq p_0,$

$H_1$ : secukinumab 150 mg is not different to GP2017 regimen with respect to proportion of subjects with no radiographic progression at Week 104

$H_2$ : secukinumab 300 mg is not different to GP2017 regimen with respect to proportion of subjects with no radiographic progression at Week 104

The primary analysis will be conducted via logistic regression with treatment as a factor and includes baseline mSASSS as a covariate. Difference in marginal response proportions with p-value and respective 95% confidence interval will be estimated from the logistic regression model.

### 2.5.3 Handling of missing values/censoring/discontinuations

Missing Week 104 data for a given subject who discontinued in the study will be imputed using an imputation model based on the observed data of subjects in the same randomized arm who also discontinued study treatment but for whom Week 104 X-ray data are available ('retrieved dropout approach', [EMA 2010](#)) and based on the observed data of the given subject.

A logistic regression model will be fitted to the Week 104 X-ray data for the retrieved dropout patients, while adjusting for treatment, baseline mSASSS and post-baseline slope in mSASSS.

The post-baseline slope is defined as the last available post-baseline change in mSASSS score divided by study day on which the X-ray was taken. Recent literature suggests that in AS patients treated with TNF inhibitors the spinal radiographic progression followed a linear course during the first 4 years of follow-up (Maas, et. al. 2017). Thus, the linearity assumption is expected to be reasonable. The covariates of baseline mSASSS and slope will be standardized to have a mean of 0 and standard deviation of 1 before model fitting.

PROC MCMC will be used for fitting the logistic regression model and multiple imputation of the Week 104 value, with weakly informative priors and model code as shown below,

```
prior beta1 ~ normal(0,sd=2);
```

```
prior beta2 ~ normal(0,sd=2);
```

```
prior beta3 ~ normal(0,sd=2);
```

```
prior beta4 ~ normal(0,sd=3);
```

```
prior beta5 ~ normal(0,sd=3);
```

```
pi = logistic(beta1*trt_GP2017 + beta2*trt_SEC150 + beta3*trt_SEC300 +  
beta4*sqrt(base_stand) + beta5*slope_stand);
```

```
model noprog ~ binary(p = pi);
```

where trt\_GP2017 – binary indicator for GP2017 40 mg

trt\_SEC150 – secukinumab 150 mg

trt\_SEC300 – secukinumab 300 mg

sqrt(base\_stand) – square root of the baseline mSASSS (standardized)

slope\_stand – the last available post-baseline change in mSASSS score divided by study day on which the X-ray was taken (standardized)

noprog – no radiographic progression at Week 104

If all post-baseline values are missing for a subject, the subject will be imputed based on a similar model as above but just based on treatment and baseline value as covariates (without the post-baseline slope variable). Subjects with a missing baseline will be excluded from the analysis.

Missing Week 104 data due to an incomplete number of interpretable locations for a given subject will be imputed using the same imputation model as described above but based on the observed data of all subjects who provided Week 104 data and based on the observed data of the given subject.

In this way multiple complete data sets are created and for each of these completed datasets the response rate will be calculated and then combined using Rubin's rule.

The potential sparsity of the retrieved data may preclude fitting the proposed model to impute the subjects with missing X-ray data at Week 104. In this case, a fallback approach will be utilized.

In case of low sample size of the retrieved dropout data (< 8 for any treatment group), the imputation model can lead to unstable imputations. In this case imputations will be performed based on a model without treatment as a covariate.

$$pi = \text{logistic}(\text{beta1} + \text{beta4} * \text{sqrt}(\text{base\_stand}) + \text{beta5} * \text{slope\_stand})$$

In case there are less than 8 retrieved dropout patients overall, the same imputation model as above will be used (without treatment as a covariate) but based on all patients (not only retrieved dropout patients).

